2.3. Number of Patients

Overall, up to 110 patients will be enrolled in the study. The sample size for this study is determined by clinical rather than statistical considerations.

In Part 1, approximately 40 patients will be enrolled, assuming up to 3 cohorts. Cohorts will consist of 6 patients each in the Phase 1b dose-finding portion of Part 1 and up to 18 patients in the Phase 2a expansion portion of Part 1 at the selected dose to be used in Part 2. Additional patients may be enrolled in the Phase 1b dose-finding portion of Part 1 if more than 1 cohort is enrolled. In Part 2, 70 patients will be randomly assigned (1:1 ratio) to 1 of 2 groups: G1T28 administered IV with E/P therapy (Group 1) or placebo administered IV with E/P therapy (Group 2). With 35 patients, the precision for point estimates in each arm is as follows: the 95% confidence interval (CI) width for binary endpoints based on Wilson score intervals are at most the observed proportion ± 0.157 . The 95% CI width for continuous endpoints using the t-distribution are the observed mean ± 0.344 *standard deviation of the endpoint.

The study will be conducted at up to 80 centers in North America and Europe.

3. ANALYSIS SETS

3.1. Definition of Analysis Sets

Data analyses will be based on the four analysis sets defined below. Analysis sets, including exclusions based on major deviations, will be reviewed and approved by G1 Therapeutics prior to the study unblinding.

3.1.1. Full Analysis Set

The full analysis set (FAS) includes all randomized patients who received at least 1 dose of study drug (etoposide, carboplatin, or trilaciclib). Analyses using the FAS will be conducted on the basis of the assigned treatment. All efficacy analyses will be assessed using the FAS. The FAS will be used for analyses of tumor response, progression-free survival (PFS) and overall survival (OS).

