### **8.3. Method of Assigning Patients to Treatment Groups**

A unique patient identification number (screen number) will be assigned to each patient who signs an informed consent form. Once a patient is determined eligible, ie, meets all inclusion/exclusion criteria, an enrollment number will be assigned by an interactive web-response system (IWRS).

Part 1 of the study (dose-finding and expansion cohorts) is open-label and there will be no randomization.

Part 2 is randomized and blinded. Patients meeting all inclusion and exclusion criteria in Part 2 will be randomized 1:1 to receive G1T28 or placebo as described in Section 8.5. Each patient will be assigned a unique randomization number, which will not be reused.

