### **8.5. Randomization and Blinding**

Part 1 is open-label and no randomization or blinding will be required.

Part 2 is randomized and blinded. Patients meeting all inclusion and exclusion criteria in Part 2 will be randomized 1:1 to receive G1T28 or placebo by an IWRS according to a randomization schedule generated by an unblinded statistician. Randomization of patients will be performed centrally and will be stratified by ECOG performance status (0 to 1 versus 2). Each patient will be assigned a unique randomization number, which will not be reused.

Each site will have an unblinded pharmacist/designee, who will have access to the treatment assignment to label and distribute the blinded study drug. The patients, investigators, other site staff involved in the clinical care of the patients, and the sponsor or designees involved in the conduct of the study will not be aware of the treatment group to which a particular patient has been randomized. If an investigator determines that a patient's assignment should be unblinded for reasons of safety, this should be discussed with the medical monitor prior to unblinding, unless an urgent and immediate intervention is required that precludes this discussion. If unblinding of the treatment assignment is necessary, the investigator will obtain the treatment assignment details from the IWRS. Any unplanned unblinding must be communicated to the project manager and study statistician for documentation in the study files and the clinical study report.

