### **13.2. General Considerations**

#### **13.2.1. Analysis Populations/Sets**

The full analysis set (FAS) includes all patients who received at least 1 dose of study drug. Analyses using the FAS will be conducted on the basis of the assigned treatment. All efficacy analyses will be assessed using the FAS and the FAS is the primary population for analysis.

The safety population includes all enrolled patients who received at least 1 dose of study drug. The safety population will be conducted on the basis of the actual treatment received. All safety analyses will be assessed using the safety population.

A per-protocol (PP) subset may also be used to analyze select endpoints and will be based on study drug exposure (compliance and/or time on study drug) and major protocol deviations. The criteria for inclusion in the PP subset will be finalized and documented prior to unblinding patients in Part 2 of the study.

The PK set will include all dosed patients in Part 1 with evaluable PK data.

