3.1.2. Safety Analysis Set

The safety analysis set includes all enrolled patients who received at least 1 dose of study drug (etoposide, carboplatin, or trilaciclib). Analyses using the safety analysis set will be conducted on the basis of the actual treatment. All safety analyses will be assessed using the safety population.

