6.2.7. Efficacy Analyses

All the efficacy variables will be summarized using descriptive statistics by cycle or visit, with the supportive data provided in patient listings. Part 1 will be summarized using only descriptive statistics. For Part 2, in addition to the descriptive summary, the between treatment comparison (trilaciclib vs placebo), if applicable, will be performed only for those prospectively-defined endpoints outlined in [Section 5.1.1](#). For these comparisons, all statistical tests will be conducted at a two-sided significance level of 20% unless otherwise specified. Where appropriate, model-based point estimates, together with their two-sided 80% CIs will be presented along with the two-sided p-value for the test. Graphical presentation of efficacy results will be appropriately performed as needed.

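### The SAP restricts the full analysis set to randomized patients, so non-randomized Part 1 has nobody in the set named for its derived efficacy endpoints, PFS and OS

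*SAP*

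**What the plan says.** SAP 3.1.1 gives two conditions for the full analysis set (FAS), randomization and at least one dose: "The full analysis set (FAS) includes all randomized patients who received at least 1 dose of study drug". The same section then says "All efficacy analyses will be assessed using the FAS" and names the FAS for tumor response, PFS and OS. SAP 6.2.8.8 repeats the FAS as the basis for PFS and OS.

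The protocol has only the dosing condition. Its section 13.2.1 reads: "The full analysis set (FAS) includes all patients who received at least 1 dose of study drug". The synopsis agrees.

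The protocol is explicit about Part 1. Section 8.3: "Part 1 of the study (dose-finding and expansion cohorts) is open-label and there will be no randomization". Section 8.5: "Part 1 is open-label and no randomization or blinding will be required".

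The SAP still plans Part 1 output. Section 6.2.7, on efficacy, says "Part 1 will be summarized using only descriptive statistics". Table 19 gives Part 1 its own display columns at 200 mg/m², at 240 mg/m² and in total. Sections 5.2.7 and 5.2.8 start PFS and OS at first dose for Part 1 and at randomization for Part 2. Section 5.2.6.4 plans response summaries for Part 1 and for the two parts pooled at 240 mg/m². The disposition table in 6.2.1, laid out by study part, counts discontinuations within the FAS.

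**The concern.** The definition is an operative rule. A programmer who applies it gets empty Part 1 columns in every table built on the FAS. One who fills those columns has departed from the SAP without a record.

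The outputs at stake serve stated secondary objectives. Both documents mark hematologic profile, transfusions, growth factor use, PFS and overall survival as objectives for the dose-finding and the expansion portions of Part 1. The neutropenia durations, the transfusion and growth factor proportions and the time to first major adverse hematologic event are all derived under SAP 5.1.1, for which the FAS is the primary set and the per-protocol set is a subset of it.

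**Working it through.** **Membership.** Let R be the randomized patients and D the patients with at least one dose. SAP 3.1.1 gives FAS = R ∩ D; Protocol 13.2.1 gives FAS = D. Protocol 8.3 and 8.5 give Part 1 ∩ R = ∅. Under the SAP rule, therefore, Part 1 ∩ FAS = ∅, however many Part 1 patients were dosed.

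**Headcount.** Inputs are from SAP 2.2 and 2.3: up to 22 in dose finding, up to 18 in the expansion, 70 randomized 1:1, and up to 110 overall.

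- The plan's totals reproduce: 22 + 18 = 40 for Part 1, and 40 + 70 = 110.
- FAS under the SAP wording: 0 + 70 = 70 at most. Under the protocol wording: 40 + 70 = 110 at most. Share excluded: 40/110 = 36%.
- Range: three full cohorts of 6 plus 18 give 36, and 36/(36 + 70) = 34%. SAP Table 19 and the footnote to Table 9 show two Part 1 dose levels. If that meant two cohorts of 6 (an assumption), Part 1 would be 12 + 18 = 30, and 30/(30 + 70) = 30%. Actual enrollment is not given.
- All patients at 200 mg/m² are excluded, because Table 19 shows that dose only in Part 1.
- The pooled 240 mg/m² group, if built on the FAS, would be 35 under the SAP wording. Under the protocol wording it would be up to (6 + 18) + 35 = 59.
- The SAP 2.3 precision figures concern 35 patients per Part 2 arm. They reproduce (largest Wilson half-width 0.157; t(0.975, 34)/√35 = 0.3435, stated as 0.344), and the FAS definition does not alter them.

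**Output by output, under the SAP wording:**

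| Output | Set named | Part 1 patients |
|---|---|---|
| Part 1 derived efficacy endpoints (SAP 5.1.1, 5.1.2) | FAS (3.1.1) | none |
| Part 1 PFS and OS | FAS (3.1.1, 6.2.8.8) | none |
| Part 1 response, FAS version (6.2.8.7) | FAS | none |
| Part 1 discontinuation counts (6.2.1) | FAS | none |
| Any Part 1 per-protocol summary (3.1.3) | subset of FAS | none |
| Part 1 response, evaluable version (3.1.4, 6.2.8.7) | Response Evaluable, built on safety set | included |
| Part 1 hematology values, grades and shifts; adverse events (6.2.8.1, 6.2.8.2) | Safety set | included |
| Part 2 trilaciclib versus placebo | FAS | not applicable; unaffected |

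The safety set admits Part 1 because it asks for enrollment, not randomization: "The safety analysis set includes all enrolled patients who received at least 1 dose of study drug".

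**Intent.** SAP 3.1.3 draws the per-protocol set from FAS patients who got the treatment they were randomized or assigned to. SAP 3.2 removes untreated patients from the FAS whether they were randomized or assigned. Both passages make sense only if assigned, non-randomized patients could be in the FAS. SAP section 7, on changes from the protocol, does not mention a narrower FAS.

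**The case against.** The best reply is that this is a one-word drafting slip with little practical risk. The context shows that Part 1 was meant to be included, the protocol definition is clear, and the SAP also counts randomized patients in its medical history and subsequent-therapy summaries (6.2.4, 6.2.6), although Table 19 covers Part 1. Part 1 efficacy is descriptive only, and every between-group test, interval and hazard ratio uses Part 2, where the SAP definition works. Section 7 lists removed endpoints and analyses, so its silence does not by itself prove a mistake.

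Most of that stands, and it limits the consequence. It does not rescue the sentence, because the SAP is the document that programmers follow and its rule conflicts with its own planned tables.

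Three further points are fair:

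- A reader might infer that all Part 1 secondary objectives lack an analysis population. The documents do not support that. Tumor response has the Response Evaluable set, and hematology values, toxicity grades, shifts and adverse events are reported on the safety set.
- PFS and OS are classed as safety endpoints in both documents, and SAP 6.2.8 puts safety analyses on the safety set in general. The FAS instruction in 6.2.8.8 is the more specific one, so this adds a conflict between sections and does not supply the missing set.
- A reader might take 36% as a loss of information from the trial's comparison. It is a planning headcount and bears on descriptive Part 1 output only. The planned sizes may themselves be dated: SAP 6.2.12 equates about 55 deaths with about 70% maturity in Part 2, which implies 55/0.70 ≈ 79 patients, not 70.

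**Conclusion.** Wrong as written. Under SAP 3.1.1 no Part 1 patient can belong to the FAS: 0 of up to about 40, or 36% of the 110 planned at most and 30% to 34% under the smaller Part 1 sizes shown above. Read literally, this empties the Part 1 summaries of the derived endpoints in SAP 5.1.1 and 5.1.2, Part 1 PFS and OS, the FAS-based Part 1 response and disposition counts, and any Part 1 per-protocol set.

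The conclusion rests on the plain wording of SAP 3.1.1 and on the protocol's statements that Part 1 is not randomized; the percentages rest on planned numbers. Nothing here suggests bias, altered error rates or lost precision in the randomized Part 2 comparison. The point deserves correction but does not threaten the trial's main comparison.

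**What to change.** Replace the sentence in SAP 3.1.1 with a definition in two limbs: the FAS comprises all Part 1 patients who received at least one dose of study drug, plus all randomized Part 2 patients who received at least one dose. Analyze by assigned dose in Part 1 and by assigned treatment in Part 2, and limit Part 2 between-group comparisons to the randomized patients. This matches Protocol 13.2.1.

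If leaving Part 1 out was intended, record it in SAP section 7 and name a separate Part 1 set for efficacy, PFS, OS and disposition. In either case, add a clause to SAP 6.2.8 saying that 6.2.8.8 is an exception to the safety-set rule.

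The cost is one sentence and one clause. No new data are needed, and no Part 2 result changes.

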3.1.2. Safety Analysis Set

The safety analysis set includes all enrolled patients who received at least 1 dose of study drug (etoposide, carboplatin, or trilaciclib). Analyses using the safety analysis set will be conducted on the basis of the actual treatment. All safety analyses will be assessed using the safety population.

3.1.3. Per Protocol (PP) Analysis Set

The per-protocol (PP) analysis set will include only those patients in FAS who have no major protocol deviations (as described in [Section 3.2](#)) and who received the treatment to which they were randomized or assigned. For patients who took the wrong treatment for part of the study, their data will be excluded from the PP analysis set. PP analysis set may be used to analyze selected endpoints to test the robustness of results. The criteria for inclusion in the PP subset will be finalized and documented prior to unblinding patients in Part 2 of the study.

3.1.4. Response Evaluable Analysis Set

The Response Evaluable Analysis Set will include all patients who are in the Safety Analysis Set and have at least 1 post-baseline tumor assessment, or have clinical progression as noted by the investigator before their first post-baseline tumor scan, or have died due to disease progression before their first post-baseline tumor scan. The response evaluable analysis set will be used for analyses of tumor response.

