5.2.7. Progression-free Survival

Since disease progression is assessed periodically, PD can occur any time in the time interval between the last assessment where PD was not documented and the assessment when PD is documented.

Hence, progression-free survival (PFS) is defined as the time (months) from date of first dose date of study drug for patients in Part 1 or date of randomization for patients in Part 2 until date of documented disease progression or death due to any cause, whichever comes first. More specifically, PFS will be determined using all the assessment data up until the last evaluable visit prior to or on the date of (i) disease progression as defined by RECIST 1.1 (Eisenhauer et al,

2009) or by clinical criteria (this will not apply to the BICR analysis); or (ii) withdrawal of consent; or (iii) receiving subsequent anti-cancer therapy, whichever is earlier.

PFS will be calculated using two response data sets: derived and BICR. For PFS determined by BICR, only progression per RECIST will be considered. For PFS as determined by derived, either clinical progression or progression by RECIST (whichever comes first) will be considered.

Death, regardless of cause, is always considered as a PD event. The detailed censoring rules for the analysis are summarized in [Table 18](#).

Table 18 Assignment of Progression or Censoring Based on Radiological Assessment

Situation	Date of Progression or Censoring	Outcome
No Baseline assessment	Date of first dose of study drug for patients in Part 1 or date of randomization for patients in Part 2	Censored
No progression	Date of last adequate radiological disease assessment	Censored
Treatment discontinuation for reasons other than disease progression	Date of last progression assessment with no documented progression	Censored
New anticancer treatment started prior to documented disease progression	Date of last adequate radiologic assessment no later than the initiation of new anticancer treatment	Censored
Disease progression	Date of the first reported progression	Progressed
Death without a PD	Date of death	Progressed
Investigator claim of clinical progression	Date of the investigator assigned PD	Progressed

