The number and percentage of patients in each category of TPR according to the investigator tumor assessment (CR, PR, SD, PD, or NE) will be presented. Also, the number and percentage of patients in each category of derived BOR (Confirmed CR, Confirmed PR, SD, PD, or NE), ORR, ORR_{UNCONFIRMED} and CBR according to the investigator tumor assessment (Confirmed CR, Confirmed PR, SD, PD, or NE) will be summarized. Detailed information of deriving tumor relevant responses is provided in [Section 5.2.6](#).

Similar analyses will be repeated based on the derived responses according to the RECIST 1.1, and based on the data from BICR. A cross tabulation of BICR BOR versus the derived BOR will be presented, by treatment group.

Estimates of response rate, along with its associated exact 95% two-sided CIs using Clopper-Pearson method will be computed for ORR and CBR within each treatment group.

DOR (investigator, derived, and BICR) will be summarized using the Kaplan-Meier method, displayed graphically when appropriate, and summarized with median, 25% and 75% percentiles, and their 95% CIs.

The binary endpoint (Yes, No) of ORR for the two treatments (trilaciclib and placebo) in Part 2 will be analyzed to compare trilaciclib and placebo using stratum-adjusted method to account for the ECOG status (0-1 vs 2) as the stratification factor. The adjusted proportion difference (trilaciclib vs placebo) and its 80% CIs will be calculated using CMH weight outlined in [Kim et al. 2013](#). The two-sided p-value will be calculated using stratified exact CMH method.

The analyses are based on the response evaluable population and FAS population. The supportive data listings will also be provided.

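### The Response Evaluable set drops patients who die before the first scan of causes other than progression, so its ORR can be inflated, and no lead set is named for the Part 2 ORR comparison

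*SAP*

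**What the plan says.** SAP 3.1.4 gives three routes into the set:

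- a scan: "The Response Evaluable Analysis Set will include all patients who are in the Safety Analysis Set and have at least 1 post-baseline tumor assessment";
- clinical progression without a scan: "or have clinical progression as noted by the investigator before their first post-baseline tumor scan";
- death without a scan, on one condition: "or have died due to disease progression before their first post-baseline tumor scan".

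It then states the purpose: "The response evaluable analysis set will be used for analyses of tumor response".

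SAP 3.1.1 also assigns tumor response to the FAS, which has no condition on scans or cause of death: "The full analysis set (FAS) includes all randomized patients who received at least 1 dose of study drug". SAP 6.2.8.7 plans the Part 2 ORR difference with an 80% CI and a stratified exact CMH p-value, and closes with: "The analyses are based on the response evaluable population and FAS population". Neither set is named as the lead.

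Under SAP 5.2.6.4, anyone without a confirmed CR or PR is coded as a non-responder. The same section asks for ORR in Part 1, in Part 2, and in the two parts pooled at 240 mg/m². Protocol 11.5.3.3 has a simpler evaluability rule (at least one postdose scan) with no exception for early death of any kind.

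**The concern.** The first on-treatment scan follows Cycle 2 (Protocol 11.5.1). Two 21-day cycles make that about six weeks, and longer if a cycle is delayed. Two treated patients may die in that window with no progression noted beforehand. If the death is attributed to progression, the patient stays in as a non-responder. If it is attributed to sepsis, bleeding or anything else, the patient disappears from the denominator. Membership therefore depends on a post-randomization outcome and on a judgment about cause of death.

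This matters here because the drug is meant to reduce myelosuppression, and the SAP itself lists treatment-related death as a component of its composite hematologic endpoint (5.1.1.11). Early death from causes other than progression is thus an event on which the arms could differ. ORR also bears on whether trilaciclib blunts the antitumor effect of chemotherapy, which Protocol 4.1 says must be avoided.

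**Working it through.** **1. The plan's own precision figures.** SAP 2.3 gives 95% half-widths for n = 35.

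- Wilson: z/(1 + z²/n) × √[p(1−p)/n + z²/(4n²)], with z = 1.96 and p = 0.5, gives 0.1572 (stated: 0.157).
- t: t(0.975; 34)/√35 = 0.3435 (stated: 0.344).

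Both reproduce.

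**2. Effect of an exclusion.** Let n be the treated patients in an arm, r the responders, and d the patients dropped because they died unscanned of another cause with no progression noted. A dropped patient has no scan, so r does not change.

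- FAS ORR = r/n
- Response Evaluable ORR = r/(n − d)
- Relative inflation = n/(n − d): 1.029, 1.061, 1.094 and 1.129 for d = 1 to 4 with n = 35

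n = 35 is the planned Part 2 arm size (SAP 2.3). The documents give neither r nor d, so both are assumptions, shown as a range.

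| FAS ORR | d = 1 | d = 2 | d = 3 | d = 4 |
|---|---|---|---|---|
| 18/35 = 51.4% | +1.5 | +3.1 | +4.8 | +6.6 |
| 21/35 = 60.0% | +1.8 | +3.6 | +5.6 | +7.7 |
| 24/35 = 68.6% | +2.0 | +4.2 | +6.4 | +8.8 |

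Entries are percentage points added to the Response Evaluable ORR.

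**3. Effect on the arm difference.** Take 20 responders in each arm, so the FAS difference is 20/35 − 20/35 = 0.

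- 1 such death on trilaciclib, 3 on placebo: 20/34 − 20/32 = 58.8% − 62.5% = −3.7 points.
- 0 against 2: 20/35 − 20/33 = 57.1% − 60.6% = −3.5 points.

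With 21 responders in each arm, 0 against 4 gives −7.7 points, and 2 against 2 gives 0.

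**4. Scale.** The unstratified 80% half-width for a difference at 57.1% with 35 per arm is 1.28 × √(2 × 0.571 × 0.429/35) ≈ 0.15, or about 15 points. A shift of 3.7 points is about a quarter of that.

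**5. Part 1.** Up to 24 patients are planned at the Part 2 dose (SAP 2.2). One exclusion multiplies ORR by 24/23 = 1.043. In the pooled group of up to 24 + 35 = 59, the factor is 59/58 = 1.017.

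**The case against.** The strongest reply is that the SAP already plans the unaffected analysis. In the FAS a randomized, treated patient who dies early of any cause stays in and is coded as a non-responder, and the result will stand beside the Response Evaluable one. For Part 2 this stands. Protocol 13.2.1 also calls the FAS the primary population. That sentence concerns efficacy, however, and Protocol 13.5.1 lists tumor response under safety, so it does not settle which ORR result leads.

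The reply is weaker for Part 1. Part 1 is not randomized (Protocol 8.3), so on the SAP's wording it has no FAS. The intent may be wider: the protocol's FAS definition does not require randomization, and SAP 3.2 speaks of patients randomized or assigned. The opening of SAP 6.2.8 sends safety analyses to the Safety set, but 6.2.8.7 specifically names the other two sets for response.

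It is also fair to say that the SAP rule is stricter than the protocol's, that ORR is not among the prospectively defined analyses in SAP Section 4, and that blinding in Part 2 limits attribution of deaths by arm.

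Three stronger readings are tempting, and the documents do not support them.

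- A reader might infer a contradiction with SAP 5.2.7, where "Death, regardless of cause, is always considered as a PD event". That rule defines an event for a different endpoint, analyzed on the FAS. An evaluability rule for response does not contradict it.
- A reader might infer that the arm with more toxic deaths must be inflated most. The set also drops patients who are unscanned for other reasons. Two toxic deaths alone give 35/33 = 1.061, while one toxic death plus two other unscanned patients gives 35/32 = 1.094. In points the response rate matters too: 26/33 − 26/35 = 4.5, but 14/32 − 14/35 = 3.75 despite more exclusions.
- A reader might infer that harm is hidden. Deaths are counted in OS, in PFS and in the summary of AEs leading to death (SAP 5.2.7, 5.2.8, 6.2.8.1). If the drug reduces toxic deaths as hypothesized, the shift favors placebo.

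**Conclusion.** The point holds for the Response Evaluable set only. Its death route conditions on cause of death, and every resulting exclusion can only raise ORR in that set. For FAS response rates from 51% to 69% in an arm of 35, the first exclusion adds about 1.5 to 2.0 points and four add 6.6 to 8.8. The arm difference moves only if exclusions or response rates differ between arms; the -3.7 points above is one illustration. All of these sizes rest on assumed death counts and response rates, and they are modest against the trial's precision.

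Two gaps make the rule worth correcting. SAP 6.2.8.7 offers two Part 2 p-values without ranking them. For Part 1 and pooled ORR, the Response Evaluable set is the only named response set that literally applies.

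**What to change.** In SAP 3.1.4, widen the death route to death from any cause before the first post-baseline scan, and state that these patients count as non-responders. In SAP 6.2.8.7, name the FAS, by assigned treatment, as the lead set for the Part 2 ORR difference and p-value, with the Response Evaluable set as supportive.

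This changes a few words and needs no new data. The cost is that ORR in the Response Evaluable set may come out slightly lower. Patients left unscanned for reasons other than death would still be outside that set, which is a further reason for the FAS to lead.
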